- 1) Untreated microinvasive or invasive cancer;
- 2) Biopsy-proven Vaginal Intraepithelial Neoplasia (VAIN) and are not undergoing treatment for VAIN;
- 3) Biopsy-proven Anal Intraepithelial Neoplasia (AIN) and are not undergoing treatment for AIN;
- 4) Biopsy-proven Cervical Intraepithelial Neoplasia (CIN) 2/3 and are not undergoing treatment for CIN;
- 5) Biopsy-proven differentiated VIN;
- 6) More than 10 weeks have elapsed between date of initial tissue biopsy for screening and day of first dose (i.e. Day 0);
- 7) Vulvar HSIL that is not accessible for sampling by biopsy instrument;
- 8) Vulvar HSIL that is not of adequate size to ensure that a visible lesion remains after biopsy;
- 9) Cervical lesion(s) that cannot be fully visualized on colposcopy due to extension high into cervical canal at screening;
- 10) History of endocervical curettage (ECC) which showed cervical HSIL indeterminate, or insufficient for diagnosis (ECC is not performed as part of study screening) and did not receive definitive treatment;
- 11) Treatment for genital warts within 4 weeks prior to screening;
- 12) Any previous treatment for vulvar HSIL (e.g. with surgery and/or imiquimod) within 4 weeks prior to screening;
- 13) Allergy to imiquimod 5% cream or to an inactive ingredient in imiquimod 5% cream;
- 14) Is pregnant, breastfeeding or considering becoming pregnant within 6 months following the last dose of investigational product;
- 15) Presence of any abnormal clinical laboratory values greater than Grade 1 per Common Toxicity Criteria for Adverse Events (CTCAE) v 4.03 within 30 days prior to Day 0 **or** less than Grade 1 but deemed clinically significant by the investigator;
- 16) Immunosuppression as a result of underlying illness or treatment including:
  - a) History of or positive serologic test for HIV at screening;
  - b) Primary immunodeficiencies;
  - c) Long term use ( $\geq 7$  days) of oral or parenteral glucocorticoids at a dose of  $\geq 20$  mg/day of prednisone equivalent (use of inhaled, nasal, otic, and ophthalmic corticosteroids are allowed);
  - d) Current or anticipated use of disease modifying doses of anti-rheumatic drugs (e.g., azathioprine, cyclophosphamide, cyclosporine, methotrexate) and biologic disease modifying drugs such as TNF- $\alpha$  inhibitors (e.g. infliximab, adalimumab or etanercept);
  - e) History of solid organ or bone marrow transplantation;

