#### 1.1.4 RECURRENT DISEASE WITH CURRENT THERAPEUTIC OPTIONS

There remains an unmet medical need with regard to effective treatment options for vulvar HSIL. Current treatment options show a significant risk of vulvar HSIL recurrence, often requiring multiple, repeat treatments. Progression to vulvar cancer following current vulvar HSIL treatments can also occur within 1 year of treatment and for up to 20 years post treatment. The current treatment options for vulvar HSIL are surgical excision, laser ablation, and off-label medical therapy. The rate of HPV-associated vulvar HSIL recurrence after surgical treatment is high; post-treatment recurrence rates exceed 30-50% with all currently available treatment regimens [12, 13].

Wide local excision is the 'preferred initial intervention' by ACOG if invasive carcinoma is suspected, and, vulvar biopsy shows vulvar HSIL. If occult invasive disease is not suspected, vulvar HSIL treatment includes surgery: wide local excision, partial vulvectomy, skinning vulvectomy, or simple vulvectomy, laser ablation. Surgical treatments are associated with disruption of normal anatomy and subsequent issues with body image and sexual dysfunction. Medical therapies have been investigated as a means to avoid these negative outcomes. Clinical trials have shown the application of topical imiquimod to be effective however it has not been approved by the U.S. Food and Drug Administration for this indication. Inconsistent treatment efficacy results have been shown with photodynamic therapy, topical cidofovir and topical 5-fluorouracil.

Vulvar HSIL may be followed (with interim observation, but, no intervention) if the patient is young, and, or, if the immune-compromised state is being corrected. Women with pathologic clear margins (no vulvar HSIL) after surgical excision have a lower, yet significant, risk of recurrence compared to women with involved margins. Laser ablation is acceptable treatment for vulvar HSIL when cancer is not suspected, although the risk of recurrence is slightly higher compared to wide local excision. Laser treatment of vulvar HSIL requires destruction of cells through the entire thickness of the epithelium including hair follicles (in hair-bearing areas of the vulva). In areas without hair, ablation should

extend through the dermis. Post-treatment recurrence rates exceed 30% (for all treatment regimens), and is higher with positive excision margins [14].

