## 2.3 EXPLORATORY OBJECTIVES AND ASSOCIATED ENDPOINTS

Exploratory Objectives	Associated Exploratory Endpoints
1. Describe the efficacy of VGX-3100, administered alone or in combination with imiquimod, at Week 74 and/or Week 96 as measured by reduction in the surface area of vulvar lesion(s), in subjects without a complete resolution at Week 48	1. Percent reduction in the cumulative surface area of the acetowhite vulvar lesion(s) as determined by the quantitative analysis of standardized photographic imaging at Week 74 and/or Week 96 compared to baseline  . Results will be classified as: no clinically significant lesion resolution (reduction in lesion area of 0-25%), partial lesion area resolution (>25% and <100% reduction), and complete lesion resolution (no visible lesion).
2. Describe the efficacy of 5 or 6 doses of VGX-3100, alone or in combination with prior imiquimod, as measured by histologic regression of vulvar HSIL	2. Proportion of subjects with no evidence of vulvar HSIL on histology (i.e. biopsies or excisional treatment) at Week 74 for subjects who receive 5 doses of VGX-3100 and at Week 96 for subjects who receive 6 doses of VGX-3100.
3. Describe the efficacy of 5 or 6 doses of VGX-3100, alone or in combination with prior imiquimod, as measured by virologic clearance of HPV-16/18	3. Proportion of subjects with no evidence of HPV-16/18 in vulvar tissue samples at Week 74 and/or Week 96.
4. Evaluate tissue immune responses to VGX-3100, and VGX-3100 with imiquimod, as measured in vulvar tissue samples	4. Assessment of CD8 + and FoxP3 infiltrating cells  .
5. Describe virologic clearance of HPV-16/18 from other anatomic locations outside the vulva	5. Proportion of subjects who have cleared HPV-16/18 on specimens from other anatomic locations without surgical intervention (inclusive of cervix, oropharynx, vagina and intra-anus) at Week 48
6. Characterize HLA haplotypes and the correlation with efficacy	6. Proportion of subjects with regression of HSIL on histology (i.e. biopsies or excisional treatment) at Week 48 visit
7. Assess skin-to-muscle, skin-to-bone, and muscle thicknesses via ultrasound measure of deltoid (or quadriceps if applicable) and the correlation of needle depth into muscle with efficacy.	7. Ultrasound-measured skin-to-muscle, skin-to-bone, and muscle thicknesses.

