### 3.2.1 DEFINITION OF RESPONDER AND NON-RESPONDER

Responder and non-responder definitions ([Table 4](#)) take into account both histopathologic regression of vulvar HSIL and virologic (HPV-16/18) clearance from tissue samples since HPV persistence is an important factor in the clinical progression of HSIL.

A treatment responder is defined as a subject with no histologic evidence of vulvar HSIL and no evidence of HPV-16 or HPV-18 in vulvar tissue at evaluation and who did not receive non-study related medication for treatment of VIN lesions. A treatment non-responder is a subject with histologic evidence of vulvar HSIL, adenocarcinoma-in-situ, or vulvar carcinoma at evaluation, and/or a subject with evidence of HPV-16/18 at evaluation,

or a subject who received non-study related medications for treatment of VIN lesions. Any case of histologically confirmed progression is considered a non-responder. Progression is defined as advancement to carcinoma by histology.

Table 4: Definition of Responder and Non-responder	
Responder	Non-Responder
Subject with no histologic evidence of vulvar HSIL a AND Subject with no evidence of HPV-16 or HPV-18 in vulvar tissue at evaluation AND Subject who did not receive non-study related medication for treatment of VIN lesions.	Subject with histologic evidence of vulvar HSIL, Adenocarcinoma-in-situ (AIS), vulvar carcinoma at evaluation  AND/OR Subject with evidence of HPV-16 or HPV-18 in vulvar tissue at evaluation  OR Subject who received non-study related medication for treatment of VIN lesions

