## 4.2 EXCLUSION CRITERIA

Subjects meeting any of the following criteria will be excluded from the study:

1. Untreated microinvasive or invasive cancer;
2. Biopsy-proven Vaginal Intraepithelial Neoplasia (VAIN) and are not undergoing treatment for VAIN;
3. Biopsy-proven Anal Intraepithelial Neoplasia (AIN) and are not undergoing treatment for AIN;
4. Biopsy-proven Cervical Intraepithelial Neoplasia (CIN) 2/3 and are not undergoing treatment for CIN;
5. Biopsy-proven differentiated VIN;
6. More than 10 weeks have elapsed between date of initial tissue biopsy for screening and day of first dose (i.e. Day 0);
7. Vulvar HSIL that is not accessible for sampling by biopsy instrument;
8. Vulvar HSIL that is not of adequate size to ensure that a visible lesion remains after biopsy;

9. Cervical lesion(s) that cannot be fully visualized on colposcopy due to extension high into cervical canal at screening;
10. History of endocervical curettage (ECC) which showed cervical HSIL indeterminate, or insufficient for diagnosis (ECC is not performed as part of study screening) and did not receive definitive treatment;
11. Treatment for genital warts within 4 weeks prior to screening;
12. Any previous treatment for vulvar HSIL (e.g. with surgery and/or imiquimod) within 4 weeks prior to screening;
13. Allergy to imiquimod 5% cream or to an inactive ingredient in imiquimod 5% cream;
14. Is pregnant, breastfeeding or considering becoming pregnant within 6 months following the last dose of investigational product;
15. Presence of any abnormal clinical laboratory values greater than Grade 1 per Common Toxicity Criteria for Adverse Events (CTCAE) v 4.03 within 30 days prior to Day 0 or less than Grade 1 but deemed clinically significant by the investigator;
16. Immunosuppression as a result of underlying illness or treatment including:
  - a. History of or positive serologic test for HIV at screening;
  - b. Primary immunodeficiencies;
  - c. Long term use ( $\geq 7$  days) of oral or parenteral glucocorticoids at a dose of  $\geq 20$  mg/day of prednisone equivalent (use of inhaled, nasal, otic, and ophthalmic corticosteroids are allowed);
  - d. Current or anticipated use of disease modifying doses of anti-rheumatic drugs (e.g., azathioprine, cyclophosphamide, cyclosporine, methotrexate) and biologic disease modifying drugs such as TNF- $\alpha$  inhibitors (e.g. infliximab, adalimumab or etanercept);
  - e. History of solid organ or bone marrow transplantation;

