### 6.16 RESTRICTIONS

The following medications and treatments are prohibited:

- Previous treatment with imiquimod for vulvar HSIL within 4 weeks prior to screening
- Long term use ( $\geq 7$  days) of oral or parenteral glucocorticoids at a dose of  $\geq 20$  mg/day of prednisone equivalent (use of inhaled, nasal, otic and ophthalmic corticosteroids are allowed)
- Disease modifying doses of anti-rheumatic drugs (e.g., azathioprine, cyclophosphamide, cyclosporine, methotrexate), and biologic disease modifying drugs such as TNF- $\alpha$  inhibitors (e.g. infliximab, adalimumab or etanercept) at screening and throughout the study
- Administration of any non-study related, non-live vaccine within 2 weeks of any study treatment or within 4 weeks of any study treatment for any non-study related live vaccine
- Blood thinners/Anticoagulants within 2 weeks of any study treatment

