## 2.3 EXPLORATORY OBJECTIVES AND ASSOCIATED ENDPOINTS

Exploratory Objectives	Associated Exploratory Endpoints
1. Describe the efficacy of VGX-3100, administered alone or in combination with imiquimod, at Week 74 and/or Week 96 as measured by reduction in the surface area of vulvar lesion(s), in subjects without a complete resolution at Week 48	1. Percent reduction in the cumulative surface area of the acetowhite vulvar lesion(s) as determined by the quantitative analysis of standardized photographic imaging at Week 74 and/or Week 96 compared to baseline  . Results will be classified as: no clinically significant lesion resolution (reduction in lesion area of 0-25%), partial lesion area resolution (>25% and <100% reduction), and complete lesion resolution (no visible lesion).
2. Describe the efficacy of 5 or 6 doses of VGX-3100, alone or in combination with prior imiquimod, as measured by histologic regression of vulvar HSIL	2. Proportion of subjects with no evidence of vulvar HSIL on histology (i.e. biopsies or excisional treatment) at Week 74 for subjects who receive 5 doses of VGX-3100 and at Week 96 for subjects who receive 6 doses of VGX-3100.
3. Describe the efficacy of 5 or 6 doses of VGX-3100, alone or in combination with prior imiquimod, as measured by virologic clearance of HPV-16/18	3. Proportion of subjects with no evidence of HPV-16/18 in vulvar tissue samples at Week 74 and/or Week 96.
4. Evaluate tissue immune responses to VGX-3100, and VGX-3100 with imiquimod, as measured in vulvar tissue samples	4. Assessment of CD8 + and FoxP3 infiltrating cells  .
5. Describe virologic clearance of HPV-16/18 from other anatomic locations outside the vulva	5. Proportion of subjects who have cleared HPV-16/18 on specimens from other anatomic locations without surgical intervention (inclusive of cervix, oropharynx, vagina and intra-anus) at Week 48
6. Characterize HLA haplotypes and the correlation with efficacy	6. Proportion of subjects with regression of HSIL on histology (i.e. biopsies or excisional treatment) at Week 48 visit
7. Assess skin-to-muscle, skin-to-bone, and muscle thicknesses via ultrasound measure of deltoid (or quadriceps if applicable) and the correlation of needle depth into muscle with efficacy.	7. Ultrasound-measured skin-to-muscle, skin-to-bone, and muscle thicknesses.

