## 4.2 EXCLUSION CRITERIA

Subjects meeting any of the following criteria will be excluded from the study:

1. Untreated microinvasive or invasive cancer;
2. Biopsy-proven Vaginal Intraepithelial Neoplasia (VAIN) and are not undergoing treatment for VAIN;
3. Biopsy-proven Anal Intraepithelial Neoplasia (AIN) and are not undergoing treatment for AIN;
4. Biopsy-proven Cervical Intraepithelial Neoplasia (CIN) 2/3 and are not undergoing treatment for CIN;
5. Biopsy-proven differentiated VIN;
6. More than 10 weeks have elapsed between date of initial tissue biopsy for screening and day of first dose (i.e. Day 0);
7. Vulvar HSIL that is not accessible for sampling by biopsy instrument;
8. Vulvar HSIL that is not of adequate size to ensure that a visible lesion remains after biopsy;

9. Cervical lesion(s) that cannot be fully visualized on colposcopy due to extension high into cervical canal at screening;
10. History of endocervical curettage (ECC) which showed cervical HSIL indeterminate, or insufficient for diagnosis (ECC is not performed as part of study screening) and did not receive definitive treatment;
11. Treatment for genital warts within 4 weeks prior to screening;
12. Any previous treatment for vulvar HSIL (e.g. with surgery and/or imiquimod) within 4 weeks prior to screening;
13. Allergy to imiquimod 5% cream or to an inactive ingredient in imiquimod 5% cream;
14. Is pregnant, breastfeeding or considering becoming pregnant within 6 months following the last dose of investigational product;
15. Presence of any abnormal clinical laboratory values greater than Grade 1 per Common Toxicity Criteria for Adverse Events (CTCAE) v 4.03 within 30 days prior to Day 0 or less than Grade 1 but deemed clinically significant by the investigator;
16. Immunosuppression as a result of underlying illness or treatment including:
  - a. History of or positive serologic test for HIV at screening;
  - b. Primary immunodeficiencies;
  - c. Long term use ( $\geq 7$  days) of oral or parenteral glucocorticoids at a dose of  $\geq 20$  mg/day of prednisone equivalent (use of inhaled, nasal, otic, and ophthalmic corticosteroids are allowed);
  - d. Current or anticipated use of disease modifying doses of anti-rheumatic drugs (e.g., azathioprine, cyclophosphamide, cyclosporine, methotrexate) and biologic disease modifying drugs such as TNF- $\alpha$  inhibitors (e.g. infliximab, adalimumab or etanercept);
  - e. History of solid organ or bone marrow transplantation;

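### Exploratory endpoint 5 disqualifies only surgery, so HPV-16/18 clearance that follows non-surgical treatment of VAIN, AIN or CIN 2/3 at the same site counts as clearance

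*Protocol*

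**What the plan says.** Section 2.3 defines exploratory endpoint 5 as the "Proportion of subjects who have cleared HPV-16/18 on specimens from other anatomic locations without surgical intervention". The full condition reads "without surgical intervention (inclusive of cervix, oropharynx, vagina and intra-anus) at Week 48". The wording is the same in protocol versions 1.0, 1.1 and 1.2, and in the synopsis.

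Three exclusion criteria (4.2 and synopsis) govern women with known disease at three of these four sites. A woman is excluded for:

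- vagina: "Biopsy-proven Vaginal Intraepithelial Neoplasia (VAIN) and are not undergoing treatment for VAIN"
- anus: "Biopsy-proven Anal Intraepithelial Neoplasia (AIN) and are not undergoing treatment for AIN"
- cervix: "Biopsy-proven Cervical Intraepithelial Neoplasia (CIN) 2/3 and are not undergoing treatment for CIN"

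Section 8.1 lists clearance outside the vulva among the exploratory efficacy analyses. Section 8.9 says only that it is analysed like vulvar clearance, that is, as a proportion with a Clopper-Pearson interval in each arm.

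**The concern.** The endpoint recognises that local treatment can clear HPV at a site and tries to set such cases aside. It does so for surgery only. The entry criteria, however, guarantee that any enrolled woman with known VAIN, AIN or CIN 2/3 is under treatment at the very site being scored, and they accept any kind of treatment. If that treatment is not surgical and HPV-16/18 is gone by Week 48, she meets the endpoint.

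What is at stake is the reading of one exploratory rate. Section 1.1.16 presents a systemic response that may clear the underlying infection as a potential benefit, and clearance away from the vulva is the result most likely to be read in that light. Both arms receive VGX-3100, so comparing the arms cannot separate its contribution from that of treatment directed at the site.

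**Working it through.** The protocol gives no figure for this endpoint, so there is none to reproduce. The check sets the rules side by side.

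**1. What disqualifies a clearance.** Under 2.3, surgical intervention and nothing else.

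**2. Who may enter.** Under exclusions 2 to 4, women with biopsy-proven VAIN, AIN or CIN 2/3 enter only while under treatment, type unrestricted. The oropharynx has no such criterion and is not affected.

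**3. Whether another rule closes the gap.**

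| Rule | Reach |
|---|---|
| 3.2.1: a responder must not "receive non-study related medication for treatment of VIN lesions" | VIN only, not VAIN, AIN or CIN |
| 6.16, imiquimod item: "Previous treatment with imiquimod for vulvar HSIL within 4 weeks prior to screening" | Vulvar HSIL, before screening; no other item covers treatment of these sites |
| 6.15 | Other medication allowed at investigator discretion, and recorded |
| 8.9 | Same method as vulvar clearance; no handling of treatment at the site |

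None does. Even if 8.9 is read as importing the responder rule, that rule stops at VIN.

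**4. Which treatments pass the filter.** Medical therapy passes on any reading. Ablation is unclear. Section 1.1.4 says "The current treatment options for vulvar HSIL are surgical excision, laser ablation, and off-label medical therapy", which sets ablation apart from excision, but its next paragraph puts laser ablation at the end of a list introduced as surgery.

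**5. Timing.** Under 3.5 the baseline sample is taken at Screening for the cervix and on Day 0 for the other sites. Vaginal or anal HPV cleared before Day 0 is therefore not scored as on-study clearance. Cervical HPV cleared between Screening and the first dose can be.

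**6. Size, by assumption only.** Let s be the share of site-positive women who had non-surgical treatment of that site, c0 the clearance without it and c1 the clearance with it. None of these is in the documents. Then

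observed rate = (1 − s) × c0 + s × c1.

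| s | c0 | observed, c1 = 40% | observed, c1 = 80% |
|---|---|---|---|
| 10% | 10% | 0.9×10 + 0.1×40 = 13% | 0.9×10 + 0.1×80 = 17% |
| 10% | 20% | 0.9×20 + 0.1×40 = 22% | 0.9×20 + 0.1×80 = 26% |
| 30% | 10% | 0.7×10 + 0.3×40 = 19% | 0.7×10 + 0.3×80 = 31% |
| 30% | 20% | 0.7×20 + 0.3×40 = 26% | 0.7×20 + 0.3×80 = 38% |

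**7. How to handle treated women.** If they are kept as not cleared, the rate is (1 − s) × c0. That is 9% or 18% at s = 10%, and 7% or 14% at s = 30%, so this choice errs low. Removing them can err high. Suppose 10 women are positive at a site, 2 clear untreated, and 2 of the other 8 are treated on study because disease persists. Keeping all gives 2/10 = 20%; removing the treated women gives 2/8 = 25%.

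**The case against.** Several points on the other side are sound.

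- **No treatment is named.** The protocol does not say how VAIN, AIN or CIN 2/3 will be treated. What it says about topical therapy concerns the vulva or genital warts. If every such woman is treated surgically, the existing filter works. A reader might infer that topical therapy at these sites is expected; the documents do not say so. What remains is that the entry rule allows any type and the endpoint screens out one.
- **Ablation may already be covered.** Given the mixed usage in 1.1.4, it cannot be said that ablation passes the filter, only that the protocol leaves this open.
- **The objective is descriptive.** Objective 5 undertakes only to describe clearance and, unlike objectives 1 to 4, does not name VGX-3100. A reader might infer that the plan attributes these clearances to VGX-3100. No passage states that; the nearest is the listing under exploratory efficacy in 8.1.
- **There are partial safeguards.** Exclusion 37 lets the investigator keep out a woman whose condition could affect an endpoint, and Day 0 sampling removes pre-dose clearance at vagina and anus. The first is discretionary and the second does not cover the cervix or treatment after Day 0.
- **A statistical analysis plan could deal with it.** It could add detail, but the protocol itself fixes the disqualifier, and applying that wording literally would keep the gap.

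**Conclusion.** The point holds as a definition that is too narrow for the protocol's own entry criteria. HPV-16/18 clearance at cervix, vagina or intra-anus after medical treatment of that site counts under endpoint 5, and so does clearance after ablation if ablation is not regarded as surgery.

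The effect could be nil or material for this one rate. The number of women entering on such treatment, its type and its effect on HPV are not given. A reader might infer that treated women make up much of the informative group, or that the bias reaches tens of percentage points. The documents support neither: a woman can be HPV-positive at a site without biopsy-proven disease there. A shift of 3/5 = 60 points, for example, would need 3 of only 5 site-positive women to be treated non-surgically, all 3 to clear because of that treatment, and none of them to clear otherwise.

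The endpoint is exploratory. Primary and secondary conclusions are untouched, so this is a worthwhile clarification and not a threat to the trial.

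**What to change.** In 2.3 and the synopsis, replace the surgery-only condition by: 'without surgical, ablative or medical treatment directed at that site between its baseline sample (Screening for cervix, Day 0 for the others) and Week 48'. Naming ablation settles the ambiguity in 1.1.4.

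Keep women with such treatment in that site's denominator and count them as not cleared. This matches 3.2.1, where non-study medication for VIN makes a woman a non-responder and does not remove her. Report the rate with treated sites excluded as a sensitivity listing, so that the reader sees both.

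Cost: one phrase in two places and one derivation from medications and procedures already recorded under 6.15. The reported clearance rate may be slightly lower, since some treated women might have cleared without that treatment. No visit, sample, entry criterion or clinical rule changes.
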